1.2 Background and rationale

Interprofessional collaboration is a crucial factor for improving quality of care, patient safety and organisational efficiency, especially in highly complex clinical-care settings such as Cardiac Intensive Care Units (CICUs/UTICs). However, although the scientific literature acknowledges the benefits of interprofessional education (IPE), it also highlights a lack of structured, validated and transferable educational models for daily clinical practice in these settings.

Systematic reviews and preliminary studies indicate that interventions based on active methodologies—such as simulation and situated learning—can improve communication between professionals, understanding of roles, mutual trust and shared decision-making, with a positive impact on the reduction of clinical errors and an improvement in interprofessional collaboration. Conversely, a lack of interprofessional cooperation is associated with preventable adverse events, poor quality of care and low job satisfaction among healthcare workers.

In response to these critical issues, the proposed study aims to develop, implement and evaluate an innovative educational model to foster interprofessional collaboration among healthcare professionals, built according to an action-research approach and integrated with digital tools to facilitate situated learning and the standardisation of contents.

The research question guiding the study is:

Can a structured interprofessional training programme based on active methodologies improve collaboration among healthcare professionals working in CICU/UTIC settings and contribute to measurable professional and care-related outcomes?

1.3 Research hypothesis

A structured training programme based on action research is more effective than traditional training in improving collaboration among healthcare professionals working in Cardiac Intensive Care Units (UTICs), including physicians, nurses, healthcare assistants (OSS), students and newly hired staff.

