1.4.2 Secondary objectives

- To compare over time (T0, T1, 6-month follow-up) the trend of the target variables (collaboration, decision-making, team and professional commitment, self-efficacy).

- To explore potential relationships between socio-demographic variables (age, profession, years of service, gender, academic degree) and educational outcomes.
- To describe the experience of the training pathway from the perspective of students and newly hired staff involved in the project.

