2.3 Interventions

2.3.1 Experimental intervention – Training phase

The training phase of the project consists of an interactive course aimed at healthcare professionals (physicians, nurses and OSS) to improve their ability to recognise and enact effective collaborative practices. Learning is based on the use of **branching scenarios**, created with the H5P software. This approach enables learners to distinguish correct practices and refine their teamwork skills. The course also provides access to additional content on techniques and procedures specific to the UTIC context, curated by expert professionals.

Branching scenarios – Learning scenarios

The branching scenarios reproduce complex and frequent clinical situations that challenge interprofessional collaboration. Each scenario has been designed with particular attention to clinical and organisational details, including:

- the clinical history of the simulated patient and their clinical pathway in the cath-lab and electrophysiology unit, in preparation for a TAVI procedure, with a diagnosis of heart failure (Annex 1);
- vital signs and diagnostic tests;
- available resources;
- clinical objectives and potential critical points.

The structure of each scenario includes:

- definition of a storyline and of the role of the professional involved;
- division into key phases, with information and possible actions, and the related consequences;
- interactive elements that enable the learner to make decisions and interact with characters or objects in the scenario;
- meaningful feedback guiding the learning process;
- multiple paths for a dynamic experience;
- assessment criteria based on the correctness of the responses.

For validation and revision of these scenarios, a team of content experts and educationalists was involved to verify the accuracy, relevance and effectiveness of the material. Pilot tests with sample users were also carried out to collect feedback on usability and clarity, and the necessary modifications were implemented.

Four training pathways are planned, each lasting six months:

1. Cath-lab pathway
2. Electrophysiology pathway
3. Heart failure pathway
4. TAVI pathway

For further details on the structure of the pathways, see Annex 8 “Pathway Sheets”.

Platform and technical implementation

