2.4 Endpoints

Description of endpoints, instruments, measurement units and frequency

- **Attitudes towards interprofessional collaboration**
 - Instrument: *Jefferson Scale of Attitudes toward Physician–Nurse Collaborative Relationships (JSAPNC)*.
 - The instrument consists of 5 dimensions: (1) shared education, (2) teamwork, (3) caring vs. curing, (4) nurse autonomy, (5) physician autonomy. It includes 15 items on a 4-point Likert scale from 1 = “strongly agree” to 4 = “strongly disagree”.
- **Perception of collaboration**
 - Instrument: *Nurse–Physician Collaboration Scale (NPCS)*.
 - The scale consists of 3 dimensions: (1) joint participation in the care-related decision-making process; (2) sharing of patient-related information; (3) cooperativeness. It includes 20 items on a 5-point Likert scale (1 = always, 2 = usually, 3 = sometimes, 4 = rarely, 5 = never).
- **Decision-making**
 - Instrument: *Collaboration and Satisfaction with Care Decisions (CSACD)*.
 - The tool measures collaboration between physicians and nurses in decision-making about patient care in relation to a specific patient. It consists of 8 items: the first seven measure interaction, and the last measures satisfaction with the decision-making process, on a 5-point Likert scale from “strongly disagree” to “strongly agree”.
- **Team and professional commitment**
 - Instrument based on items adapted from Ellemers et al. (1995), Cadinu & Reggiori (2002) and Le Blanc et al. (2010).
 - Total of 17 items: 12 items for **professional commitment** (e.g. “In general, I am happy to be part of my professional category”) and 5 items for **team commitment** (e.g. “I am satisfied to be a member of this unit/team”), on a 5-point Likert scale from 1 = strongly disagree to 5 = strongly agree.
- **Self-efficacy**
 - Instrument: “Personal accomplishment” subscale of the *Maslach Burnout Inventory (MBI)*, Italian adaptation by Vanin & Castelli (2003) and Sirigatti & Stefanile (1993), based on Maslach & Jackson (1981).
 - Composed of 5 items evaluating perceived competence and personal accomplishment at work, using a 5-point Likert scale from 1 (strongly disagree) to 5 (strongly agree). Example item: “I feel very competent in my work.”

Data collection for these endpoints will occur at three time points: before the start of the training (T0), at the end of the training (T1), and six months after completion of the programme (T2).

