2.6 Sample size

A convenience sample will be used, consisting of professionals who agree to participate in the training process (planned: physicians: 5; nurses: 30; OSS: 8; nursing students: 5; medical students: 5).

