3.2 Data analysis

- **Reliability and validity:** At T0, T1 and T2 Cronbach's alpha and McDonald's omega will be calculated for each (sub)scale. Where appropriate, the factor structure will be confirmed through confirmatory factor analysis (CFA) with assessment of measurement invariance (configural → metric → scalar) prior to longitudinal comparison.
- **Data preparation and quality:** data cleaning, coding, reverse-scoring of items; exploration of missing data, outliers and distributions (histograms, Q–Q plots); inspection of floor and ceiling effects; documentation of the data dictionary.
- **Descriptive analysis and responsiveness:** descriptive statistics for T0, T1 and T2 (mean, SD, median, IQR) for total and subscale scores. Suggested graphs: spaghetti plots (individual trajectories), box/violin plots and mean lines with 95% CI over time. Responsiveness to change: calculation of Cohen's d (T1–T0; T2–T0; T2–T1) and Standardized Response Mean (SRM) as indices of change, with interpretation according to literature conventions; where possible, definition/search of MCID.
- **Main analysis – Linear mixed models (LMMs):** For each outcome, a linear mixed model will be used with time as a within-subject factor.
 - Dependent variable: continuous outcome score.
 - Fixed effects: Time (T0 as reference; levels T1, T2).
 - Random effects: random intercept for participant; if data allow, random slope for Time.
 - Covariance structure: unstructured or AR(1) for equally spaced measures; REML estimation.
 - Planned contrasts: T1–T0 (immediate effect), T2–T0 (maintenance), T2–T1 (decay/maintenance).
 - Effect measures: standardised β , marginal and conditional R^2 ; conversion to d from LMM estimates with 95% CIs.

- Assumptions/diagnostics: normality of residuals and homoscedasticity; graphical inspection and robust tests in case of violations.
- Covariates (recommended): age, seniority, profile (physician, nurse, OSS, student/new hire), concurrent educational exposures.
- Interactions: Time × Profile; Time × Seniority, to analyse differential impacts.
- Clustering: if relevant (e.g. shifts/teams), addition of a group-level random effect.

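### Section 1.3 claims superiority over traditional training, but the protocol follows one trained group and plans only time contrasts, so the hypothesis cannot be tested.

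*Protocol*

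**What the plan says.** Section 1.3, the only section headed as the research hypothesis, is comparative: "A structured training programme based on action research is more effective than traditional training in improving collaboration among healthcare professionals".

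The rest of the protocol is before-after:

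- **Research question (1.2):** "Can a structured interprofessional training programme based on active methodologies improve collaboration among healthcare professionals working in CICU/UTIC settings". No other training is named.
- **Objectives (1.4.1, 1.4.2):** the primary objective is the effectiveness of the pathway, with no comparator. The comparison among the secondary objectives is in time: "To compare over time (T0, T1, 6-month follow-up) the trend of the target variables".
- **Design and eligibility (1.5, 2.2.1):** one longitudinal cohort. Evaluation is limited to professionals who finished the training and remain in the unit at six months, and finishing it is also an inclusion criterion for them.
- **Intervention (2.3.1):** only an experimental intervention is described: "The training phase of the project consists of an interactive course aimed at healthcare professionals (physicians, nurses and OSS". Its four pathways differ by clinical topic.
- **Time points (2.4):** "before the start of the training (T0), at the end of the training (T1), and six months after completion of the programme (T2".
- **Sample (2.6):** "A convenience sample will be used, consisting of professionals who agree to participate in the training process", broken down by profession only.
- **Analysis (3.2):** time is the fixed effect. "Planned contrasts: T1–T0 (immediate effect), T2–T0 (maintenance), T2–T1 (decay/maintenance". "Interactions: Time × Profile; Time × Seniority, to analyse differential impacts".

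**The concern.** A claim that one training works better than another needs information on what the other achieves. Here everyone who can enter the staff evaluation has received the programme. A change from T0 to T1 or T2 describes that trained group and does not show what traditional training would have achieved over the same period. The hypothesis can be neither confirmed nor refuted by any result the study can produce.

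The practical risk lies in reporting. Section 5.8 contemplates peer-reviewed publication. With section 1.3 as the formal hypothesis, a favourable T1–T0 change could be presented as support for superiority over traditional training.

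**Working it through.** The protocol gives no power calculation or effect size, so there is no figure to reproduce. The check is whether a comparison of trainings exists anywhere in the plan.

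**1. Search for a comparator**

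| Element | Section | Comparison of trainings? |
|---|---|---|
| Research question | 1.2 | No |
| Objectives | 1.4 | No; over time, and by socio-demographic variables |
| Design and evaluated group | 1.5 | No; completers of the programme |
| Eligibility of staff | 2.2.1 | No; completion required |
| Intervention | 2.3.1 | No; one programme, four topics |
| Time points | 2.4 | No; anchored to this programme |
| Sample | 2.6 | No; 0 planned for traditional training |
| Contrasts | 3.2 | 0 of 3 |
| Interactions | 3.2 | 0 of 2 |
| Hypothesised results | 5.9 | 0 of 6 |

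Planned numbers from 2.6: staff 5 + 30 + 8 = 43; students 5 + 5 = 10; total 43 + 10 = 53.

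**2. Can the model in 3.2 estimate a training effect?**

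The planned fixed part has three columns: intercept, T1 and T2. Testing section 1.3 would need three more: Training, Training × T1 and Training × T2. With Training = 1 for everyone,

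- Training = intercept,
- Training × T1 = T1,
- Training × T2 = T2.

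The matrix then has 6 columns but rank 3, for the 43 staff (43 × 3 = 129 rows) and for all 53 (53 × 3 = 159 rows). The number of training coefficients that can be estimated is 3 − 3 = 0. Adding participants adds rows but not rank. This follows directly from having one trained group; it restates the design problem in terms of the model.

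For n = 53 the check treats the 10 students as trained. Section 2.6 counts them among those who agree to the training, whereas 2.3.1 aims the course at physicians, nurses and OSS. If the students were not trained, they still would not be a traditional-training group.

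**3. What a real comparison would need (illustration only)**

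The protocol supplies no inputs. Assume two-sided alpha 0.05, 1:1 allocation, one outcome, independent participants and no dropout. With d the standardised difference, n per group = 2(1.960 + 0.842)² / d² for 80% power.

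| Assumed d | n per group for 80% power | Power, 53 split 1:1 | Power, 43 staff split 1:1 |
|---|---|---|---|
| 0.2 | 393 | 0.11 | 0.10 |
| 0.5 | 63 | 0.44 | 0.37 |
| 0.8 | 25 | 0.83 | 0.75 |

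The smallest d detectable with 80% power is about 0.77 with 53 people and 0.85 with 43. The finding does not depend on these figures.

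**The case against.** The strongest reply is that one sentence is out of step with an otherwise coherent before-after protocol. No sample size, endpoint or contrast depends on the comparative wording, and 5.9 judges success without a comparator. That is true, and it is why the repair is cheap. It does not make the hypothesis testable, and the hypothesis is the statement against which results will be read.

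A second reply is that the study does record other training: previous courses on collaboration (1.5) and concurrent educational exposures (3.2). These data exist, but they are meant for subgroup or adjusted analyses. They would compare backgrounds among people who all took the programme, and so provide no group given traditional training instead.

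A third is that T0 stands for the state under traditional training. The protocol does not say so, nor does it describe such training. Even on that reading, T1–T0 would measure the change when this programme is added, not the difference from giving traditional training over the same period.

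Two cautions about the rewording do stand. Section 5.9 speaks of results at the end of the intervention, so the T2 part of a new hypothesis rests on 1.5 and 3.2. And because 1.5 limits evaluation to completers still in the unit, the new hypothesis should refer to that group.

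**Conclusion.** Section 1.3 is wrong as written and must be changed. Superiority over traditional training is not identified by this design at any sample size: 0 of 53 planned participants are assigned to traditional training, and 0 of 3 contrasts and 0 of 2 interactions address it. The conclusion needs no numerical assumption, only that the protocol describes the whole design. An unseen analysis plan could not rescue it, because the comparator is absent from eligibility, sampling and assessment timing, not just from the analysis text.

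**What to change.** In section 1.3, remove the comparison with traditional training and state a within-participant hypothesis. For example: among the participants evaluated under section 1.5, mean scores improve from T0 to T1 and remain improved at T2 relative to T0. The T1–T0 and T2–T0 contrasts already in 3.2 address this.

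Add one sentence, in 1.5 or 3.2, saying that the results are uncontrolled pre-post changes and do not support a comparison with traditional training.

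This costs two edits to the text. Participants, instruments, time points and models are unchanged. What is lost is the superiority claim, which the study could not support.

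If the sponsor wants to keep that claim, the alternative is a concurrent traditional-training group and a Group × Time contrast. That means a different design, and under the illustrative assumptions above the planned 53 people split in two would give power of about 0.44 at d = 0.5.

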1.4 Objectives

1.4.1 Primary objective

To assess the effectiveness of an interprofessional training pathway with an action-research approach in improving, among healthcare professionals working in the CICU/UTIC:

- perception of interprofessional collaboration
- collaborative attitudes
- involvement in shared decision-making
- self-efficacy
- team and professional commitment

1.4.2 Secondary objectives

- To compare over time (T0, T1, 6-month follow-up) the trend of the target variables (collaboration, decision-making, team and professional commitment, self-efficacy).

- To explore potential relationships between socio-demographic variables (age, profession, years of service, gender, academic degree) and educational outcomes.
- To describe the experience of the training pathway from the perspective of students and newly hired staff involved in the project.

1.5 Study design

The study design is longitudinal and prospective and provides for the evaluation of the effectiveness of an interprofessional training pathway through three assessment points: before the intervention (T0), immediately after completion of the programme (T1) and six months later (T2). The evaluation will be carried out exclusively on healthcare professionals who have completed the training and are still working in the unit at the time of the six-month follow-up.

The intervention consists of a training programme specifically designed to improve collaboration among healthcare professionals working in Cardiac Intensive Care Units (UTICs), using active and context-based methodologies.

At each time point the same indicators are collected, including perception of collaboration, attitude towards collaboration, decision-making, team and professional commitment, and self-efficacy. These dimensions constitute the primary outcomes of the intervention and are observed to measure the evolution over time of behaviour and professional perceptions of the staff involved.

The design also takes into account several socio-demographic and professional variables—such as age, gender, years of service, professional role and previous participation in courses on collaboration—that may influence the impact of the training pathway. For students, the degree course (medicine or nursing) and academic year are also recorded. These factors are collected at baseline (T0) and will be used for possible subgroup or adjusted analyses.

Before the start of the training pathway, a detailed guide on how to access the platform will be distributed.

Overall, the design aims to assess not only the immediate effectiveness of the training path but also its sustainability over time, by observing changes in professional behaviours and attitudes six months after the intervention.

2. Methodology: participants, interventions and endpoints

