2.2 Eligibility criteria

2.2.1 Inclusion criteria

Participants meeting all of the following criteria will be included in the study:

- Healthcare professionals (physicians, nurses and healthcare assistants/OSS) employed in the Cardiac Intensive Care Unit (UTIC) of the University Hospital of Parma.
- Healthcare professionals who have completed the training pathway and are still working in the unit at the time of the six-month follow-up.
- Medical and nursing students who have carried out or are carrying out a clinical placement within the UTIC.
- Ability to use a computer or mobile device, essential for participating in the online training activities (e.g. Moodle, H5P).
- Provision of written informed consent before initiation of any study procedure.

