2.7 Recruitment

On the training days, the Principal Investigator or a delegate will present the project and request informed consent from physicians, nurses, OSS, medical students and nursing students affiliated with the UTIC of the University Hospital of Parma.

3. Methodology: data collection, management and analysis

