5.4 Informed consent

Informed consent will be obtained by the PI or a delegate when healthcare professionals and medical/nursing students first enter the UTIC unit.

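### Inclusion and the evaluated set of staff depend on two events after baseline (finishing the training, still in post at six months)

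*Protocol*

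**What the plan says.** The restriction appears twice in the protocol. Section 1.5 (Study design) defines who is evaluated: "The evaluation will be carried out exclusively on healthcare professionals who have completed the training and are still working in the unit" at six months. Section 2.2.1, whose criteria must all be met, lists as its second bullet: "Healthcare professionals who have completed the training pathway and are still working in the unit at the time of the six-month follow-up".

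Consent comes much earlier. The same list requires "Provision of written informed consent before initiation of any study procedure". Section 2.7 says "On the training days, the Principal Investigator or a delegate will present the project and request informed consent", and section 5.4 says "Informed consent will be obtained by the PI or a delegate when healthcare professionals and medical/nursing students first enter the UTIC unit".

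Sections 2.4 and 3.1 place T0 before training, T1 at its end and T2 six months later. On the length of training, section 2.3.1 says "Four training pathways are planned, each lasting six months". It does not say how many pathways each person takes.

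The primary objective in section 1.4.1 concerns effectiveness "in improving, among healthcare professionals working in the CICU/UTIC", with no condition on completion or retention. Section 1.5 adds that "the design aims to assess not only the immediate effectiveness of the training path but also its sustainability over time". Section 3.2 plans a linear mixed model with contrasts T1–T0, T2–T0 and T2–T1, and does not repeat the restriction.

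**The concern.** An inclusion criterion has to be verifiable at enrolment. This one is not: a person can consent, complete T0 and T1, and become ineligible afterwards by changing jobs.

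The rule also works against the stated aims. The immediate effect is measured by T1–T0, yet people with both values would be left out of it for a reason that arises after T1. In a set chosen by later events, an apparent gain, absence of gain or decay may partly reflect who finished and stayed. The study follows a single group, so no comparator would expose this.

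A related wording conflict concerns students. Section 1.3 counts them among healthcare professionals, whereas section 2.2.1 lists them apart from physicians, nurses and healthcare assistants. It is therefore unclear whether the 10 planned students (section 2.6), who share a profile level in the section 3.2 model, belong to the evaluated set.

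**Working it through.** **Timing.** Consent precedes any procedure, including T0. With one six-month pathway, T1 falls about 6 months after T0 and T2 about 6 + 6 = 12 months after T0. The criterion is therefore settled no earlier than about 12 months after the decision it is meant to govern.

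**Numbers.** Section 2.6 plans 5 + 30 + 8 = 43 staff, plus 5 + 5 = 10 students. It gives no completion rate, turnover rate, SD or correlation, so there is no figure of the protocol's own to reproduce. Every input below other than the 43 is an assumption.

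**Records lost.** With completion c and retention r, the evaluated number is 43 × c × r, and the discarded T0–T1 pairs number 43 × c × (1 − r).
- With c = 0.9 and r = 0.8, 43 × 0.9 × 0.8 ≈ 31 are evaluated. About 12 people with T0 are dropped, of whom 43 × 0.9 × 0.2 ≈ 8 also have T1.
- Over c from 0.8 to 1.0 and r from 0.7 to 0.95, the evaluated number runs from 24 to 41.

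**Precision of T1–T0.** In units of the score SD, with an assumed T0–T1 correlation of 0.6, SE = √(2 × (1 − 0.6)/n). If all loss falls after T1:
- all 43 used: √(0.8/43) = 0.136
- 80% kept (34.4): √(0.8/34.4) = 0.152
- 70% kept (30.1): √(0.8/30.1) = 0.163

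**Bias in the restricted set.** This was simulated with 4,000,000 trivariate-normal participants and no true change. Correlations were 0.6 (T0–T1), 0.5 (T0–T2) and 0.6 (T1–T2), and retention was logistic in one score. The strong case keeps 70%, with a retention log-odds of 1.0 per SD. Bias in score SD:

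| Staying depends on | T1–T0 | T2–T0 | T2–T1 |
|---|---|---|---|
| T0 score | −0.10 | −0.13 | −0.03 |
| T1 score | +0.10 | 0.00 | −0.10 |
| T2 score | +0.03 | +0.13 | +0.10 |
| No score | 0 | 0 | 0 |

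In 20,000 simulated studies of 43 people, nominal 5% paired t tests rejected in 9–11% on the contrasts with a bias of 0.10 SD or more. In the mild case (80% kept, log-odds 0.3) the largest bias was 0.03 SD and rejection stayed at about 5%. With correlations varied from 0.4/0.3/0.4 to 0.8/0.7/0.8, the largest bias ran from 0.18 down to 0.08 SD in the strong case and from 0.04 down to 0.02 SD in the mild case.

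**Bias when all available data are used (strong case).**

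| Staying depends on | T1–T0 | T2–T0 | T2–T1 |
|---|---|---|---|
| Observed T0 or T1 score | 0.00 | 0.00 | 0.00 |
| T1 score, T1 missing for leavers | +0.17 | +0.08 | −0.09 |
| T2 score, T0 and T1 observed | 0.00 | +0.16 | +0.16 |
| T2 score, T1 also missing | +0.08 | +0.20 | +0.12 |

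Using all data removes the bias when loss depends on scores already recorded. When loss tracks unseen scores it does not, and several contrasts are then worse than in the restricted set.

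**The case against.** The restriction may be a deliberate completer analysis that was placed under eligibility by mistake. The inclusion list cannot be strictly conjunctive, since nobody is both an employed professional and a student on placement, and section 3.2 does not carry the restriction forward. A fixed set of completers also has a rationale: all three contrasts then describe the same people, which suits the sustainability aim. Nothing in the protocol suggests that finishing or staying relates to scores. The bias may be nil, and the recommended primary analysis does not always reduce it. The precision gain is small: with 90% completion and 80% in post, the detectable effect at 80% power and two-sided 5% moves from (1.960 + 0.842)/√31.0 = 0.50 to 2.802/√38.7 = 0.45 SD of change.

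Much of this stands as a limit on the size of the problem. It supports reporting a labelled completer set beside the all-available analysis. It does not support keeping later events as an inclusion criterion, or applying the completer set to T1–T0 alone. A statistical analysis plan could define analysis sets, but it could not repair an inclusion criterion fixed in the protocol. The student question is secondary. Section 1.5 records students' course and year for possible subgroup or adjusted analyses, which suggests they are meant to be analysed and makes the conflict with its own restriction more visible.

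**Conclusion.** The concern holds and should be fixed. The eligibility fault is a matter of logic and does not depend on any loss rate: two conditions that post-date T0 are used to decide inclusion and evaluation. The practical effect is uncertain because the protocol gives no loss rate. Under the base-case correlations, the bias ranges from zero (unrelated loss) through about 0.03 SD (mild) to 0.13 SD (strong), reaching 0.18 SD with weaker correlations. Its sign depends on which score drives retention. The cost in precision is modest, an SE of 0.14 against 0.15–0.16 SD for T1–T0 if loss falls after T1.

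**What to change.** - Delete the second inclusion bullet in section 2.2.1 and the sentence in section 1.5 that restricts the evaluation. Define eligibility only by facts known at T0, and read the participation-related exclusion in section 2.2.2 the same way, so that it cannot remove non-completers later.
- Make all consenting eligible participants with a T0 questionnaire the primary analysis set, and fit the planned mixed model to all available T0, T1 and T2 data.
- Keep non-completers still in post on the questionnaire schedule, with T1 at the scheduled end of the pathway and T2 six months later. Sections 1.5, 2.4 and 3.1 currently tie both to the end of training. For people who leave the unit, use the data collected up to leaving.
- Retain completers still in post as a labelled sensitivity analysis and report both analyses.
- Report numbers and reasons for loss, and compare the T0 scores of stayers and leavers.
- Reconcile sections 1.3, 1.5, 2.2.1, 2.6 and 3.2 on whether students are evaluated.

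The cost is wording, one line on timing, and existing questionnaires for non-completers still in post. No new instruments or recruits are needed. The drawback is that the all-available analysis relies on loss depending only on observed scores. That is why T1 should be collected from non-completers and both analyses shown.
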